9. ADVERSE EVENT REPORTING

9.1. Reporting Requirements non-CTIMPs

The collection and reporting of Adverse Events (AEs) will be in accordance with the Research Governance Framework for Health and Social Care and the requirements of the Health Research Authority (HRA). Definitions of different types of AEs are listed in the table of abbreviations and definitions. The Investigator should assess the seriousness and causality (relatedness) of all AEs experienced by the trial participant this should be documented in the source data with reference to the protocol.

9.2. Adverse Events (AE) non-CTIMPs

All medical occurrences which meet the definition of an AE should be reported. Please note this includes abnormal laboratory findings.

Peri-operative and post-operative complications experienced by the participants are the primary outcomes of the LAVA study. Complications arising from the interventions will be collected on the relevant CRFs.

As these events are well characterised, it is highly unlikely that this trial will reveal any new safety information relating to this intervention. The recording of selected AEs will therefore not affect the safety of participants or the aims of the trial. As such the following will not be classed as adverse events and so do not need to be reported as AEs:

- Haemorrhage \geq 1L
- Surgical Complications (any factor that comprises the Clavien-Dindo grade [II-IV] with or without hospitalisation or prolongation of existing hospitalisation)
- Anaesthetic complications
- Additional Medication required above that normally expected
- Emergency presentations / admissions
- Routine re-presentations / admissions for pre-planned events
- Prolonged hospitalisation without an associated adverse event
- Vaginal bleeding
- Pelvic organ prolapse
- Abdominal pain [cyclical / non-cyclical, and dyspareunia]
- Conditions / symptoms arising from altered bowel or bladder function

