Adverse Event	AE	Any untoward medical occurrence in a participant or clinical trial subject participating in the trial which does not necessarily have a causal relationship with the intervention received
Related Event		An event which resulted from the administration of any of the research procedures
Serious Adverse Event	SAE	An untoward occurrence that: 
 • Results in death • Is life-threatening • Requires hospitalisation or prolongation of existing hospitalisation (with exceptions – see section 9.2) • Results in persistent or significant disability or incapacity • Or is otherwise considered medically significant by the Investigator
Unexpected and Related Event		An event which meets the definition of both an Unexpected Event and a Related Event

Unexpected Event		The type of event that is not listed in the protocol as an expected occurrence
Source data		All information in original records and certified copies of original records of clinical findings, observations, or other activities in a clinical trial necessary for the reconstruction and evaluation of the trial
Birmingham Clinical Trials Unit	BCTU	The co-ordinating centre for the trial

TRIAL SUMMARY

Title Laparoscopic Versus Abdominal hysterectomy (LAVA) trial

Objectives To determine the clinical and cost-effectiveness of laparoscopic hysterectomy compared to open abdominal hysterectomy for women with a benign gynaecological condition

Trial Design A parallel, open, non-inferiority, multicentre, randomised controlled, expertise-based surgery trial with integrated health economic evaluation and an internal pilot with an embedded qualitative process evaluation.

Participant Population and Sample Size 3250 women who require a hysterectomy for a benign gynaecological condition

Eligibility Criteria Women with benign gynaecological conditions requiring a hysterectomy and who are suitable for either surgical technique are eligible for inclusion. The intervention is laparoscopic hysterectomy and the comparator is open, abdominal hysterectomy.

Interventions Laparoscopic hysterectomy compared to open abdominal hysterectomy

Outcome Measures Summary (full details given in section 8.1)

- **Primary** – Major surgical complications up to six completed weeks post-surgery
- **Key secondary** - Time from surgery to resumption of usual activities using the personalised PROMIS-SF (Patient-Reported Outcomes Measurement Information System Physical Function) questionnaire

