8.1.2. Primary Outcome

Major surgical complications. These will be objectively ascribed and largely in accordance with the validated and widely used Clavien-Dindo classification of surgical complications²⁴. They will be defined as any of the following up to and including six full weeks post-surgery: i) all Clavien-Dindo grade III-V complications ii) Clavien-Dindo grade II complications of pulmonary embolus or blood transfusion or; iii) haemorrhage \geq 1L or; iv) major adverse anaesthetic event (see table below).

The most commonly anticipated major surgical complications are:

- Haemorrhage \geq 1 L
- Blood transfusion
- Bladder injury
- Ureteric injury
- Bowel injury
- Vascular injury
- Unplanned removal of any other organ
- Any other complication not covered requiring surgical, endoscopic or radiological intervention
- Pelvic haematoma requiring radiological or surgical intervention
- Pelvic abscess requiring radiological or surgical intervention
- Life-threatening complication requiring admission to HDU/ITU

However, other less common major surgical or anaesthetic complications may arise and these will be ascribed in accordance with the appropriate Clavien-Dindo classification.

Definition of major surgical complications in the LAVA trial

Major haemorrhage	Haemorrhage \geq 1L
Clavien-Dindo grade II	Pulmonary embolus, blood transfusion
Clavien-Dindo grade III	Complication requiring surgical, endoscopic or radiological intervention
Clavien-Dindo grade IV	Life-threatening complication requiring management on a High Dependency Unit (HDU) / intensive therapy unit (ITU)*
Clavien-Dindo grade V	Death
Major anaesthetic event	Anaphylaxis, awareness, nerve injury (including epidural/spinal anaesthesia), hypoxic brain injury, malignant hyperthermia, iatrogenic complication (e.g. pneumothorax from central line, limb ischaemia from arterial line)

*Non-life threatening elective or precautionary admission to an HDU (e.g. because of medical co-morbidities) post-operatively will not be considered a grade IV complication.

Complication data occurring during and up to 6 weeks following hysterectomy will be collected from the relevant case report forms completed by the local research team:

- Day of Surgery CRF
 - Detailing the type of major peri-operative complications
- Post-operative inpatient CRF
 - Detailing the type and timing of major surgical complications occurring during inpatient stay up until hospital discharge)

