9.3. Serious Adverse Adverts (SAE) non-CTIMPs

All events which meet the definition of serious, and that are not excluded above, will be collected and recorded as SAEs. These will be reported to the trials office immediately and within 24 hours of being made aware of the event.

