9.9. Data Monitoring Committee non-CTIMPs

The independent Data Monitoring Committee (DMC) will review all SAEs.

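### The SAE definition limits the section 9.2 exceptions to hospitalisation, but 9.2 to 9.4 remove whole events, so non-fatal disabling complications escape SAE reporting and the rule for some deaths is unclear

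*Protocol*

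**What the plan says.** The definitions table at the front of the protocol gives five grounds for calling an event serious. One carries a cross-reference to exceptions: "Requires hospitalisation or prolongation of existing hospitalisation (with exceptions – see section 9.2". The others (death, threat to life, disability, and medical significance in the investigator's view) carry none. The disability ground reads in full: "Results in persistent or significant disability or incapacity".

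Section 9.2 gives a list of events and its effect: "As such the following will not be classed as adverse events and so do not need to be reported as AEs". Among the items are:

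- haemorrhage of one litre or more, with no limit on outcome;
- "Surgical Complications (any factor that comprises the Clavien-Dindo grade [II-IV] with or without hospitalisation or prolongation of existing hospitalisation";
- "Anaesthetic complications", with no grade, outcome or time limit.

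Section 9.3 then states: "All events which meet the definition of serious, and that are not excluded above, will be collected and recorded as SAEs". Section 9.4 repeats the same carve-out for SAEs judged possibly related to the intervention.

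Two other places bear on this. Section 8.1.2 defines a major anaesthetic event to include "Anaphylaxis, awareness, nerve injury (including epidural/spinal anaesthesia), hypoxic brain injury, malignant hyperthermia". Section 9.9 says: "The independent Data Monitoring Committee (DMC) will review all SAEs".

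**The concern.** The two parts of the protocol answer the same question differently. By the definitions table, only an event that is serious because of hospitalisation can be exempt. By section 9, a listed event is exempt on any ground, because it is no longer an adverse event at all. Section 9.1 sends investigators to the definitions table to judge seriousness, so sites are given both texts.

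The whole individual-case safety route hangs on the SAE form: the 24-hour report (9.3, 9.5.2), the chief investigator's independent view of seriousness and causality and the expectedness assessment of related events (9.6), and the DMC's review of SAEs (9.9). A listed event that leaves a woman permanently harmed would miss all of these.

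SAEs are also a trial outcome. Section 13.2.2 compares them with a chi-squared test, and section 13.2 allows that test without multiplicity adjustment. If up to 50 hospitals apply different readings, the count does not mean the same thing everywhere. Section 11.3 also uses low SAE reporting as a trigger for on-site monitoring, and that signal is harder to read if sites differ for this reason.

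**Working it through.** No formula applies; the check sets the definition against the reporting rules, case by case.

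| Case | Definitions table | Section 9.2 list | Result under 9.3 and 9.4 |
|---|---|---|---|
| Complication serious only through a longer stay or readmission | Exception allowed | Listed | Not an SAE; the texts agree |
| Non-fatal anaesthetic complication with lasting disability | Serious; no exception | Anaesthetic item, no limit | Not an SAE; the texts conflict |
| Grade II-IV surgical complication with lasting disability | Serious; no exception | Surgical item | Not an SAE; the texts conflict |
| Grade IV surgical complication, no lasting disability | Serious (life-threatening); no exception | Surgical item, IV named | Not an SAE; the texts conflict, but the exemption looks intended |
| Surgical death (grade V) without major haemorrhage | Serious; no exception | Outside the surgical item | SAE; the texts agree |
| Death with haemorrhage of 1 L or more | Serious; no exception | Haemorrhage item has no limit, surgical item stops at IV | Ambiguous |
| Death from an anaesthetic complication | Serious; no exception | Anaesthetic item has no limit | Ambiguous |

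**Disability rows.** These need no interpretation. Section 8.1.2 names hypoxic brain injury and nerve injury as anaesthetic events, and both can leave permanent harm. The anaesthetic item in 9.2 covers them, and 9.3 then removes them. Being related to surgery does not bring them back, because 9.4 repeats the exclusion.

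**Death rows.** The surgical item stops at grade IV, which suggests that deaths were meant to stay reportable. The haemorrhage and anaesthetic items are separate and have no such stop. Against that, 8.1.2 says that less common surgical or anaesthetic complications are also given a Clavien-Dindo grade, and there death is grade V. The protocol does not say whether that grade overrides the separate items.

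**What is still captured.** The complication CRFs in 8.1.2 record these events up to six weeks, as primary-outcome data. Section 13.3 says the interim analyses are likely to include the primary outcome, at least annually. Six weeks is the window of those CRFs, not of the 9.2 list, which has no time limit.

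**The case against.** The strongest reply is that section 9 is the operative rule and the definitions table only defines terms. Section 9.3 openly filters the definition, so a site that works from section 9 has one instruction. The exclusion is also deliberate and reasoned: these complications are the primary outcome, the protocol calls them well characterised, they have their own CRFs, and section 3.5 rates the trial as no riskier than standard care.

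Much of this stands. It justifies keeping expected complications out of expedited reporting. It does not explain why the definitions table confines the exception to hospitalisation, or why one item stops short of death while its neighbours do not. Outcome CRFs also do not replace a 24-hour report or an individual causality assessment.

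Four stronger readings are tempting and are not supported.

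- *Anaesthetic deaths are certainly not SAEs.* The grading language in 8.1.2 allows the opposite reading; the text is ambiguous.
- *About 183 women are affected.* That is 0.06 × 3055 = 183.3, using the 6% rate and the pre-attrition sample size in 13.1 and assuming equal arms. It counts every expected major complication, including haemorrhages and transfusions that need be neither fatal nor disabling, and grade V deaths that the surgical item does not remove.
- *A 15-day ethics report is lost each time.* Section 9.7.1 covers only unexpected and related SAEs. Several of these events are named in 8.1.2 and might be judged expected, so an SAE form need not have led to such a report.
- *The DMC would not know.* Annual review is a minimum, the DMC may meet sooner or in an emergency (16.5), and immediate notification of a significant safety issue (9.7.2) does not depend on SAE status.

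Allocation is also minimised by recruiting centre, so each site should contribute to both arms. A site's reading changes the number of SAEs but does not in itself favour one arm.

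**Conclusion.** The contradiction is real and should be corrected. It is certain for non-fatal anaesthetic complications and grade II-IV surgical complications that leave lasting disability: they are serious by definition and excluded by the reporting rules. For deaths linked to anaesthesia or major haemorrhage, the finding is ambiguity, not proven exclusion.

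The loss is limited to expedited individual reporting, the chief investigator's review, the DMC's case-level view, and a consistent SAE count across sites. Primary-outcome capture up to six weeks is unaffected. The protocol gives no rate for fatal or disabling events, so the number at stake cannot be derived; it is probably small. The conclusion rests on a literal reading of 9.2 to 9.4 and on no numerical assumption.

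**What to change.** Reconcile the definitions table with sections 9.2, 9.3 and 9.4.

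1. Add to 9.2 that a listed event meeting the death criterion or the disability criterion of the SAE definition is still reported on an SAE form under 9.3, whichever item of the list it falls under. This settles the disability cases and removes the ambiguity over deaths.
2. Amend the SAE definition so that it says the other listed events are recorded on the outcome CRFs and not as SAEs. If the sponsor wishes to keep grade IV complications exempt, the definition should say so, because the life-threatening criterion now carries no exception.
3. Align the cross-references in 9.3 and 9.4 with the revised 9.2.

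The cost is one protocol amendment, site training and a small number of extra SAE forms. The complication CRFs and the primary analysis do not change.

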 - Satisfaction with hysterectomy (5-point Likert scale ranging from very satisfied to very unsatisfied)
 - Symptoms of urogenital prolapse using the Pelvic Organ Prolapse Symptom Score (POP-SS) questionnaire²⁸ (score ranging from 0 no symptoms to 28 maximum symptoms)
 - Bladder function using Urogenital Distress Inventory (UDI)^{29, 30} questionnaire (score ranging from 0 good to 100 bad)
 - Bowel function using Defecatory Distress Inventory (DDI)³¹ questionnaire (overall score ranging from 0 good to 100 bad)
 - Sexual function using the Sexual Activity (SAQ) questionnaire³² (pleasure score ranging from 0 worst to 18 best; discomfort score

ranging from 0 worst to 6 best; habit score ranging from 0 worst to 3 best)

- Quality of life score using EuroQol-5D-5L questionnaire (as scored above)
 - Quality of life score using EuroQol-5D-5L visual analogue scale (as scored above)
 - Body image using the Body Image Scale (BIS) questionnaire³³ (score ranging from 0 no disturbance to 30 maximum disturbance)
 - New gynaecological symptoms (abdominal pain [cyclical, non-cyclical and dyspareunia] and vaginal bleeding; yes/no)
 - Contact with Community Social and Clinical Care Services i.e. outpatients or emergency visits, and hospital services e.g. re-presentations, re-admissions, outpatient appointments and further medical treatment, time away from normal activities (collect to inform that Health Economic assessment [section 15]; not reported separately)
- Throughout: Serious adverse events (see section 9)

* Questionnaire may be completed at home if patient discharged on the same day as surgery

**The latter two time-points will only be collected for participants who reach these times prior to the study closes after all patients have been followed up for 12 months.

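### The section 9.2 adverse-event exclusions have no end date, but the complication forms that justify them stop at 6 weeks, so late non-fatal surgical complications reach no safety outcome

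*Protocol*

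**What the plan says.** Protocol section 9.2 gives two reasons for not collecting certain events as adverse events: they are well characterised, and they are recorded elsewhere ("Complications arising from the interventions will be collected on the relevant CRFs"). It then states that "the following will not be classed as adverse events and so do not need to be reported as AEs". The list covers haemorrhage of 1 L or more, surgical complications ("any factor that comprises the Clavien-Dindo grade [II-IV] with or without hospitalisation or prolongation of existing hospitalisation"), anaesthetic complications and "Emergency presentations / admissions", among other items. None carries a time limit.

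Section 9.3 applies the list to serious events: "All events which meet the definition of serious, and that are not excluded above, will be collected and recorded as SAEs". Section 9.4 keeps the exception in force from entry to the anaesthesia suite until the woman leaves the study. Its rule that related SAEs are reportable however late they occur is also restricted to events that are not excluded.

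On the forms, section 8.1.2 says: "Complication data occurring during and up to 6 weeks following hysterectomy will be collected". It names three: day of surgery, post-operative inpatient, and 6-week complication and re-presentation. In section 8.1.3.2, minor complications, re-presentation and readmission also end at 6 weeks. Hospital contacts recorded at 12, 24 and 36 months carry the note "collect to inform that Health Economic assessment [section 15]; not reported separately".

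**The concern.** An exclusion from adverse-event reporting is sound while another instrument captures the same events. Here the exclusion lasts to study exit and the other instrument ends at week 6, so after that the stated reason no longer applies.

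This matters because SAEs are the protocol's only safety measure of serious events beyond 6 weeks. Section 8.1.3.2 lists them as an outcome collected throughout. Section 13.2.2 compares them between arms with a chi-squared test, and section 13.2 exempts that test from multiplicity adjustment on safety grounds. Sections 9.9 and 13.3 make them the safety material for the DMC. Expedited reporting to the ethics committee under section 9.7.1 also depends on an event being classed as an SAE.

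The background (sections 1.1 and 1.2) names urinary tract injury as the known disadvantage of the laparoscopic route. Section 8.1.2 anticipates bladder, ureteric and bowel injury. If such an injury is recognised or repaired after week 6, it falls under the Clavien-Dindo exclusion. It would then be missing from the one comparison meant to show late serious harm by surgical route.

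**Working it through.** The protocol gives no figure to reproduce on this point. The check follows each type of event through the reporting rules on either side of week 6.

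| Event | Up to 6 weeks | After 6 weeks |
|---|---|---|
| Non-fatal Clavien-Dindo III-IV surgical complication | Primary outcome, on complication forms (8.1.2) | Excluded from AEs (9.2) and SAEs (9.3, 9.4); no complication form |
| Grade II pulmonary embolus or transfusion | Primary outcome (8.1.2) | Excluded, as above |
| Other grade II complication | Minor complication if on the 8.1.3.2 list | Excluded, as above |
| Major anaesthetic event | Primary outcome (8.1.2) | Excluded, as above |
| Re-presentation or readmission | Secondary outcome (8.1.3.2) | Service-contact form only, for economics |
| Death | Primary outcome (grade V) | Still an SAE: grade V lies outside the excluded range II-IV |
| Serious event not on the 9.2 list | SAE | SAE |

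Three places might have closed the gap.

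1. The schedule in section 8.2.10 has an SAE row running to month 12. SAEs are defined by section 9, so the row omits the excluded events.
2. The open-ended rule for related SAEs in section 9.4 covers only events that are not excluded.
3. The definition of a serious event makes its hospitalisation criterion subject to section 9.2, so that criterion does not restore the excluded events either.

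The schedule shows no complication form after 6 weeks.

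The time during which the exclusions apply but no complication form does is follow-up minus 6 weeks:

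- 12 months: 52 - 6 = 46 weeks, and 46/52 = 88%.
- 24 months (only women who reach it before study close): 104 - 6 = 98 weeks, and 98/104 = 94%.
- 36 months (same restriction): 156 - 6 = 150 weeks, and 150/156 = 96%.

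These are shares of calendar time. The protocol gives no rate for complications arising after 6 weeks, so they cannot be turned into a number or proportion of events missed.

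**The case against.** The strongest reply is that the exemption is deliberate and proportionate. The trial compares two routine operations, is classed as no riskier than standard care (section 3.5), and exempts well-characterised events. Most of the commonly anticipated complications in section 8.1.2 are operative or early. That supports sparing sites expedited paperwork. It does not explain why the exemption outlasts the forms said to replace it.

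A second reply is that section 9.2 introduces the list by referring to complications that form the primary outcome, which ends at 6 weeks, so the complication item might be read as sharing that limit. The reading is possible but not secure. Section 9.4 applies the exception until study exit, and the same list contains long-term conditions such as prolapse. A site following the text would not report a late complication.

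A reader might also infer more than the protocol supports:

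- **That the SAE table will be nearly empty, or that late differences will show as zero.** Late deaths and unlisted serious events stay reportable. Readmissions and further treatment are recorded for the economic evaluation, which section 15 reports in disaggregated form. Prolapse, bladder, bowel, pain and bleeding outcomes are collected in both arms at 12 months. None of these is graded or assessed for causality as a complication, but late harm is not wholly invisible.
- **That emergency admission for any cause is removed.** The item may name only the admission and not the diagnosis behind it. The serious-event definition ties the section 9.2 exceptions to the hospitalisation criterion alone. An unlisted diagnosis that is life-threatening, disabling or medically significant could still qualify. The wording is ambiguous, and a blanket removal is not established.
- **That 88% of complications are missed.** That figure is time, as shown in the working.
- **That the DMC sees no complication data.** Section 13.3 also gives it the primary outcome. What it lacks is complications after week 6.

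**Conclusion.** The point holds within limits. Read together, sections 9.2 to 9.4 and 8.1.2 leave non-fatal grade II-IV surgical complications, and anaesthetic complications, outside every safety outcome once they first arise or are recognised after week 6. The gap covers weeks 7 to 52 for all participants, and longer for those followed to 24 or 36 months. How many events fall in it is unknown.

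The conclusion assumes that sites apply the exclusion list as written, without a time limit. If a 6-week limit was intended, the text needs to say so. The primary outcome, which ends at 6 weeks by definition, is unaffected; the loss is to the between-arm SAE comparison and to the DMC's view of late harm. Reporting scope and form windows are fixed in the protocol, and a statistical analysis plan cannot supply events that were never collected as safety data.

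**What to change.** Reconcile section 8.1.2 with sections 9.2 to 9.4 as follows.

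1. Limit the complication and emergency-admission exclusions in 9.2 to events within 6 weeks of surgery that are captured on the complication forms.
2. State that the emergency presentation or admission item does not exclude the serious diagnosis underlying it.
3. After week 6, report as SAEs those complications and unplanned admissions that meet the serious definition and of which the site becomes aware.
4. Tabulate by arm, for the DMC and the final report, the re-presentations and readmissions already collected on the 12-month form. Amend the note in 8.1.3.2 that now keeps them from separate reporting.

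The cost is a protocol amendment and some extra SAE forms. No new visit is required, but ascertainment after week 6 will be incomplete, because the schedule then has only participant questionnaires and the SAE row, with no site record review. The late tabulation should be presented with that limitation stated.

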- 6 week post-surgery complication and representation CRF
 - Detailing the type and timing of major post-operative complications, as well as any reattendance and / or readmissions to hospital up to 6 weeks post-surgery, will be recorded. The data will be acquired by the local research team from scrutiny of the hospital case-notes and / or follow up consultation (if conducted routinely at approximately 6 weeks post-hysterectomy). The "6 week follow up patient completed CRF" that reports overnight admission following hysterectomy will also be checked and corroborated by the TMG for consistency; see below.

The TMG will collate "6 week follow up patient completed CRFs" that report overnight admission following hysterectomy. If the corresponding "6 week post-surgery and representation CRF" does not record a major surgical complication then the local PI will be contacted by the TMG and asked to provide additional information to explain the apparent discrepancy (e.g. oversight by the local research team, invalid patient response, re-admission another hospital etc.), and the reason for the overnight hospital admission and any additional treatments. The local PI will be asked to record their response on a Data Clarification Form.

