8.1.3.2 Other secondary outcomes

- Surgical outcomes:
 - Duration of operation, (minutes)
 - Estimated blood loss, (ml)
- In hospital stay:
 - In hospital post-operative pain using a Numerical rating scale (NRS) (with 0 indicating no pain to 10 indicating maximum pain)*, measured daily
 - Total analgesia use*
 - Overall quality of recovery score taken from the Quality of Recovery 15 (QoR-15) questionnaire²⁵ (with 0 indicating worst recovery and 10 indicating best recovery), measured at approximately 24 hours post-operation*
 - Time from operation to discharge in days (the day of operation will be assumed to be day 1. i.e. discharge on day 2 = 2 days). Each part of a day will count as a whole day, e.g. discharge after 2.5 days = 3 days)
- Up to 14 days after surgery:
 - post-operative pain using a Numerical rating scale (NRS) (with 0 indicating no pain to 10 indicating maximum pain), measured daily
 - Total analgesia use

- Up to 6 weeks post-surgery:
 - Minor complications (Haemorrhage 500mL to ≤ 1 L; pyrexia [presumed infection] requiring antibiotics; pain uncontrolled with usual analgesic management; urinary retention requiring re-catheterization; catheterisation for longer than 72 hrs; pelvic haematoma NOT requiring radiological or surgical intervention; pelvic abscess NOT requiring radiological or surgical intervention; wound infections/complications managed at the bedside or on the ward)
 - Representation to hospital
 - Readmission to hospital
 - Use of health services
 - Time away from normal activities

- 6 weeks post-surgery:
 - Quality of life score using EuroQol-5D-5L questionnaire²⁶ (with -0.285 indicating worst possible value and 1.0 as best possible value)
 - Quality of life score using EuroQol-5D-5L visual analogue scale (with 0 indicating worst possible score and 100 as best possible score)

- 12 weeks post-surgery:
 - Quality of life score using EuroQol-5D-5L questionnaire²⁶ (with -0.285 indicating worst possible value and 1.0 as best possible value)
 - Quality of life score using EuroQol-5D-5L visual analogue scale (with 0 indicating worst possible score and 100 as best possible score)
 - Time from surgery to work (if working) in days
 - Work productivity and activity impairment scores using WPAI-GH questionnaire²⁷ (absenteeism score; presenteeism score; work productivity loss score; activity impairment score – all scored 0 good to 100 bad) at 12 weeks only

- 12/24/36 months post-surgery:**

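### Section 9.2 exempts every grade II surgical complication from AE/SAE reporting, but the major and minor definitions count only some of them, so an unlisted one treated in the index stay reaches no named complication or SAE outcome

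*Protocol*

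**What the plan says.** Three parts of the protocol bear on this.

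- **Reporting.** Section 9.2 first asks for all adverse events, then gives a list of exceptions introduced by "As such the following will not be classed as adverse events and so do not need to be reported as AEs". One item is "Surgical Complications (any factor that comprises the Clavien-Dindo grade [II-IV] with or without hospitalisation or prolongation of existing hospitalisation". Another is "Additional Medication required above that normally expected". The stated reason is that peri- and post-operative complications are trial outcomes and are collected on the CRFs. Section 9.3 extends the exceptions to serious events: "All events which meet the definition of serious, and that are not excluded above, will be collected and recorded as SAEs". Section 9.4 repeats the carve-out.
- **Major complications (Section 8.1.2).** The primary outcome takes "all Clavien-Dindo grade III-V complications" in full, but from grade II only "Clavien-Dindo grade II complications of pulmonary embolus or blood transfusion", plus haemorrhage of 1 L or more and major anaesthetic events. The 6-week site form is described there as "Detailing the type and timing of major post-operative complications, as well as any reattendance and / or readmissions to hospital"; the inpatient form is likewise described for major complications.
- **Minor complications (Section 8.1.3.2).** This is an enumerated list. It includes "pyrexia [presumed infection] requiring antibiotics; pain uncontrolled with usual analgesic management; urinary retention requiring re-catheterization; catheterisation for longer than 72 hrs", together with haemorrhage between 500 mL and 1 L, pelvic haematoma or abscess managed without intervention, and wound problems dealt with on the ward. It has no 'other' entry. Representation and readmission up to 6 weeks are separate secondary outcomes.

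**The concern.** Taking complications out of AE/SAE reporting is reasonable when the outcome CRFs pick them all up. That holds only if the exemption is no wider than the outcome definitions replacing it. For grade II it is wider: the exemption names the whole grade, while the outcomes name selected events.

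The trial exists to compare the complications of two surgical routes. A complication that needed treatment, and that may have prolonged the stay and so met the protocol's own definition of serious, could be left out of that comparison by a site following the text exactly. The Data Monitoring Committee might not see it either: Section 9.9 gives the committee the SAEs, and Section 13.3 foresees the primary and key secondary outcomes plus SAEs. This is a rule about what sites collect. A statistical analysis plan cannot recover an event that sites were told they need not report.

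**Working it through.** The protocol states no figure for these events, so the check is a side-by-side reading. The table covers the period up to 6 weeks after surgery and takes Section 9.2 literally.

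| Event | AE/SAE (9.2, 9.3) | Major (8.1.2) | Minor (8.1.3.2) | Other 6-week outcome |
|---|---|---|---|---|
| Grade V | Reportable (outside the II-IV bracket) | Yes | n/a | n/a |
| Grade III-IV | Exempt | Yes, all | n/a | n/a |
| Pulmonary embolus, transfusion (grade II) | Exempt | Yes | n/a | n/a |
| Pyrexia given antibiotics, haematoma or abscess without intervention, ward-managed wound infection (if grade II) | Exempt | No | Yes | n/a |
| Any other grade II, after discharge | Exempt | No | No | Representation or readmission, cause unnamed |
| Any other grade II, wholly within index stay | Exempt | No | No | None by name |

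1. For grades III and IV the exemption and the primary outcome match, so nothing is lost. Grade II is where they part.
2. Some of grade II is covered by the two named major events, and probably more by the drug-treated items on the minor list. Only the unlisted remainder is at issue.
3. Deep vein thrombosis serves as an example. The protocol names it nowhere. Treated with drugs alone, it meets neither the grade III row of the Section 8.1.2 table (surgical, endoscopic or radiological intervention) nor the grade IV row (life-threatening, managed on HDU/ITU). Placing it in grade II is an assumption.
4. If such an event arises after discharge and brings the woman back, the representation and readmission outcomes count the attendance. The Section 8.1.2 cross-check of patient-reported overnight admissions may prompt a query, but it looks for missed major complications.
5. If the event is treated wholly within the index stay, there is no readmission to count. Time to discharge may lengthen, without giving the reason.
6. Other Section 9.2 items could exempt the same event again: additional medication, emergency presentations and admissions, and conditions arising from altered bowel or bladder function.

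For scale only: Section 13.1 plans 3055 women before the loss-to-follow-up inflation, or 3055 / 2 = 1527.5 per arm. Each 1% incidence of unlisted grade II events would be 0.01 × 1527.5 ≈ 15 women per arm, and 3% would be 0.03 × 1527.5 ≈ 46. The assumed 6% control rate of major complications gives 0.06 × 1527.5 ≈ 92. The 1% and 3% are illustrations without support in the protocol. They are also upper figures for the complete loss, since events after discharge can surface as attendances.

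**The case against.** Four counter-arguments deserve weight.

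**Section 9.2 may mean less than it says.** Its first three exemptions (haemorrhage, Clavien-Dindo grades, anaesthetic complications) follow the Section 8.1.2 table, whose grade II row holds only pulmonary embolus and transfusion. If grade II is meant in that trial-specific sense, other events stay reportable and the gap closes. Section 9.2 does not say which sense applies. Sites could read it either way, which is itself a reason to reconcile the text.

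**The CRFs may hold the data.** The 'major' wording sits under the primary outcome and may describe only how that outcome is obtained. Section 8.2.3 has the Day of surgery CRF record the Clavien-Dindo grade without restriction, Section 8.2.10 lists complications during the hospital stay, and Section 8.2.5 describes a post-surgery complication form. The CRFs are not shown, so it is not established that these events go unrecorded. This stands, but no outcome definition counts the event even where raw data exist.

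**Stronger readings are not supported.** A reader might infer that all grade II events other than the two named are lost; the minor list shows otherwise. A reader might infer that they reach no safety outcome at all; representation and readmission contradict that for events after discharge. A reader might take the exemption as a prohibition; the text says only that reporting is not needed. A reader might also infer that milder grade I events must be reported while worse ones need not be. The bracket does begin at II, but the protocol never defines grade I, so the point does not rest on this.

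**Differential loss is not shown.** Section 1.1 expects a longer stay after abdominal surgery and mentions mobility restriction in overweight and obese women. A reader might conclude that more events vanish in one arm. The protocol gives neither the rate nor the timing of unlisted events by arm.

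**Conclusion.** The concern holds as a mismatch between Sections 8.1.2, 8.1.3.2 and 9.2. Read plainly, the protocol exempts all of grade II from AE/SAE reporting while its complication outcomes cover part of grade II. What falls through completely is the unlisted grade II complication treated within the index stay. After discharge, what is lost is the identity of the event rather than the attendance.

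This rests on two assumptions: that grade II in Section 9.2 means the whole grade, and that there are drug-treated events of that grade on neither list. The number of women affected cannot be derived from the protocol, and no bias between arms is demonstrated. The primary outcome, the sample size and the non-inferiority test are untouched; what suffers is the completeness of the secondary and safety comparison. It should be corrected because the rule, followed as written, omits treated complications in a trial designed to compare them.

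**What to change.** Reconcile the three sections with two changes.

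1. Add to the minor-complication outcome in Section 8.1.3.2, and to the existing inpatient and 6-week site CRFs, an item such as *any other Clavien-Dindo grade II complication not counted as major (specify)*.
2. Limit the surgical-complication exemption in Section 9.2 to events recorded on a CRF as a major (8.1.2) or minor (8.1.3.2) complication, so that any other event meeting a seriousness criterion is reported as an SAE. Then check that the remaining exemptions (additional medication, emergency admissions, altered bowel or bladder function) do not take the same events out again.

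The cost is a protocol wording change, one line on two forms already in use, and slightly more data entry at sites. The primary outcome definition does not change.
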